5.1 Inclusion criteria

- Admission to DIFFICULT-TO-WEAN UNIT at Forcilles Hospital;
- Presence of a tracheotomy on admission to Difficult-to-Wean Unit;

- Presence of invasive ventilation on admission to Difficult-to-Wean Unit with a predicted duration of > 48 hours;

- Patient aged at least 18 years at the time of inclusion;
- Affiliation to or beneficiary of a social security scheme;
- Oral, free, informed and express consent of the patient or a relative.

5.2 Non-inclusion criteria

- Known pregnancy ;
- Person subject to a legal protection measure;
- Person under guardianship or curatorship;
- Refusal of access to data by the patient or the designated trusted person.

5.3 Recruitment procedures

[figure not shown]
Patients will be recruited prospectively and consecutively from the Difficult-to-wean Unit (=Post-ICU settings) of the Forcilles Hospital following an ICU stay. One of the investigating physicians will identify the patient upon confirmation of transfer from an ICU to the Difficult-to-Wean Unit.

6 Research design

6.1 Type of study

This is a prospective, monocentric, interventional cohort study with minimal risk and constraints falling under 2° of article L.1121-1 of the Public Health Code (Category 2, Jardé law).

6.2 Outline of the research

6.3 Provisional timetable for the research

The duration of recruitment will be 24 months with a follow-up of patients for 1 month, i.e. a total duration of the study estimated at 25 months.

- PPC submission: November 2020;
- Start of inclusion: January 2021;
- Duration of the inclusion period: 2 years;
- Duration of participation of each patient: 1 month (average length of stay in DIFFICULT-TO-WEAN UNIT);
- End of inclusions: January 2023;
- Total duration of the research: 2 years and 1 month;

- Communication in congresses: National and international congresses in intensive care and anesthesiology;

- Publication: July 2023

7 Description of the usual post-ICU settings management

There will be no change to the usual management of Difficult-to-Wean Unit inpatients under this protocol.

7.1 Medical and nursing procedures

Medical procedures for diagnostic or therapeutic purposes and nursing care will be carried out in the usual way, respecting hygiene measures. These procedures consist of all the treatments and care usually provided to a patient hospitalised in a Difficult-to-Wean Unit, mainly

- Treatment of respiratory failure;
- Treatment of co-morbidities;
- Measures to prevent and treat complications related to inpatient care.

Similarly, in order to be able to evaluate and adapt the management of the patient in the Difficult-to-Wean Unit as best as possible, an entry biological assessment is carried out within 48 hours of admission. The biological assessment includes the following elements: haemoglobin, leucocytes, lymphocytes, neutrophils, troponin, renal function (urea, creatinine, GFR), metabolic function (calcium, magnesium, phosphate, TSH, cortisol at 8 hours, 25(OH)D) and inflammatory function (albumin, CRP)

Morphological characteristics (height, weight) are measured in the usual way on admission of the patient in order to adapt the nutritional management.

7.2 Weaning from mechanical ventilation

Patients admitted to Difficult-to-Wean Unit will be tracheostomised and invasively ventilated in a difficult or prolonged weaning situation (4).

Causes of weaning failure or decanulation (cardiac, respiratory, neurological, muscular, etc.) will be treated according to good practice guidelines.

7.3 Early rehabilitation

Patients admitted to the DIFFICULT-TO-WEAN UNIT receive early rehabilitation as part of the prevention and treatment of complications related to ICU hospitalisation.

Rehabilitation will be carried out in the usual way by the teams of physiotherapists, speech therapists, nurses and care assistants (according to their respective skills). The rehabilitation intervention is prescribed by the doctor. In the absence of a specific indication from the doctor, the physiotherapist or speech therapist chooses the type of rehabilitation act according to the patient's condition.

The frequency of rehabilitation will depend on the doctor's prescription if it specifies it, on the habits and resources of the department and on the patient's condition.

7.4 ICU-acquired muscle weakness assessment

ICUAW is assessed using the MRC score, performed by the ward physiotherapists on admission of the patient. The MRC score is widely used in resuscitation patients to detect acquired muscle weakness (19)(20). The score assesses 3 muscle groups for each of the upper and lower limbs. Each muscle group will be scored between 0 and 5 according to the voluntary strength developed. An overall score out of 60 is calculated (Appendix 2).

7.5 Assessment of swallowing disorders

As part of the patient's speech and language therapy, an assessment of swallowing disorders is carried out by a member of the speech and language therapy team when the patient tolerates several hours of deventilation per day.

For this purpose, we will use the modified Cowling swallowing score which consists of 4 points (Appendix 3): no disorder, abnormality to solids, abnormality to liquids, abnormality to liquids and solids.

The assessment is based on the detection of liquid, solid or liquid and solid false routes by ingestion techniques of coloured or uncoloured liquids/foods with the search for these potential false routes in the airways via tracheal aspirations through tracheostomy.

7.6 Decanulation bronchial fibroscopy

As part of the patient's laryngeal and pulmonary assessment prior to tracheostomy decanulation, a bronchial fibroscopy will be performed as a matter of routine by the department's physicians.

The objectives of this fibroscopy are described in Appendix 4. The objectives are the evaluation of the ENT sphere with the search for oedema of the hypopharynx, the arytenoids, the evaluation of the mobility of the vocal cords and the evaluation of the sensitivity of the hypopharynx. The assessment is followed by an evaluation of the trachea, including the positioning of the tracheostomy cannula, the existence of tracheal ring fractures, the search for granuloma, tracheomalacia and bronchomalacia.

7.7 Decanulation decision

The decision to decanulate follows a progressive de-ventilation and assessment protocol based on respiratory and extra-respiratory criteria:

Respiratory criteria :

- Patient under mechanical ventilation 24 hours a day: the tracheostomy cannula is a nonwindowed or a windowed cannula with a low pressure cuff of the Silhey® LPC, Bivona® Mid-Range Air Cuf or Portex® Blue-Line Ultra type; allowing to limit the risks of tracheal lesions due to the cuff;

- Patient under mechanical ventilation <18h/24h or dislocated > 6h/24h (with the cuff of the tracheostomy cannula deflated): the cannula is changed for a non fenestrated high pressure cuffed cannula such as Bivona® TTS. This type of cannula is with a plated silicone cuff and is very well tolerated and facilitates speech therapy exercises. The size of the tracheostomy cannula is sometimes reduced to facilitate the exercises but this is not consensual and is more a matter of practice specific to each department.

- Patient discharged during the day: generally 8am-6pm, then progressive lengthening of the time before nocturnal reventilation (plateau at 8pm-10pm-00am).

- Patients discharged during the day and early evening: this discharging is continued throughout the night. Complete 24-hour de-ventilation is recorded when the patient is de-ventilated for 48 hours without the need for re-ventilation.

- Patient is deventilated 24 hours a day: the next step consists of placing a plug over the tracheostomy orifice. Thus, the patient's "classical" respiratory tract is used and the patient is in a respiratory situation equivalent to a patient without a tracheostomy tube.

Extra-respiratory criteria:

After 48 hours with the cannula plugged, in the absence of a respiratory event, the patient is considered decanulable. Various assessments are carried out to ensure that there are no potentially negative predictive factors:

- Speech therapy: pharyngolaryngeal oedema is assessed by phonation exercises. These exercises can also be used to assess vocal cord and/or glossal damage. Swallowing of liquids and solids is tested.

- Physiotherapy: neuromuscular and diaphragmatic function (MRC score, ultrasound) are assessed.

Decanulation is possible when the patient does not have a major swallowing disorder, pharyngo-laryngeal oedema or laryngeal sensitivity disorder with risk of passive false routes (salivary or food) and when muscle recovery, absence or recovery of diaphragmatic dysfunction and trunk tone are satisfactory.

These extra-respiratory parameters are intimately linked to respiratory progress. Indeed, without satisfactory neuromuscular recovery, without orthophonic reinforcement of swallowing, the patient will not be able to progress on the ventilatory level.

Once all the parameters are satisfactory and a decanulation fibroscopy does not reveal any anomaly contraindicating decanulation, the tracheostomy cannula is removed. To do this, the cannula is simply removed and an occlusive dressing is placed over the tracheal orifice. This usually closes within 3 to 5 days.

8 Assessment procedures added by the research

The collection of data and the examinations necessary for the evaluation criteria will be carried out by one of the investigators not involved in the management of the patient.

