4.1 Main outcome

Successful decanulation is defined as maintenance of spontaneous ventilation in the absence of recanulation, acute use of non-invasive ventilation (NIV) or death within 48 hours.

Factors potentially associated with successful decanulation will be collected prospectively:

- Severity factors related to the ICU stay:

o Total number of oro-tracheal intubations ;

o Number of days on mechanical ventilation;

o Curarisation or not with duration

o Whether or not prone sessions were performed with duration;

o Whether or not ECMO was used as a back-up;

o Number of pneumopathies acquired under mechanical ventilation;

o IGS2 ;

- Ventilatory factors :

o Number of failed extubations before tracheostomy in the ICU;

o Duration of mechanical ventilation before tracheostomy in the ICU (days);

o Type of tracheostomy used: percutaneous or surgical;

o Time to first attempt at Difficult-to-Wean Unit de-ventilation (days);

o Time to 24-hour at Difficult-to-Wean Unit de-ventilation (days);

o Time from 24-hour deventilation to successful DIFFICULT-TO-WEAN UNIT decanulation (days);

o Number of ventilator-associated lung diseases (VAPs) in at Difficult-to-Wean Unit;

- Respiratory factors:

o Ultrasound lung ventilation score on admission to at Difficult-to-Wean Unit;

o Diaphragmatic dysfunction on admission to at Difficult-to-Wean Unit;

o Bronchial fibroscopy abnormalities prior to decanulation;

- Extra-respiratory factors:

o Confusional state on admission to at Difficult-to-Wean Unit (CAM-ICU, Appendix 1);

o Existing swallowing disorders (assessed after 6 hours of ventilation) by the modified Cowling swallowing score (18);

o Oral status on admission to at Difficult-to-Wean Unit (normal, moderately impaired, dilapidated, no teeth);

o ICU-Acquired muscle weakness (MRC score) on admission to at Difficult-to-Wean Unit;

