4.2 Secondary outcomes

- Proportion of successful decanulation among all included patients (prevalence of successful decanulation);

- Proportion of successful weaning from IV among all included patients (prevalence of successful weaning from IV). Successful weaning from invasive ventilation is defined as the absence of invasive ventilation >48h ;

- The same factors potentially associated with successful weaning from IV will be collected as described in section 4.1.

- Collection of biological parameters within the first 48 hours of admission to Difficult-to-Wean Unit: haemoglobin, leukocytes, lymphocytes, neutrophils, troponin, renal function (urea, creatinine, GFR), metabolic function (calcium, magnesium, phosphate, TSH, cortisol at 8 hours, 25(OH)D) and inflammatory function (albumin, CRP);

- Ventilatory parameters on admission to Difficult-to-Wean Unit: ventilatory mode (VAC, VSAI), ventilatory settings (FiO2, PEP, AI, FR, Vt);

- Demographic characteristics of these patients during Difficult-to-Wean Unit hospitalisation: mortality, length of hospitalisation, duration of invasive ventilation.

- Nutritional assessment by evaluation of grip strength by Handgrip at admission and discharge from the Difficult-to-Wean Unit, by evaluation of the stage of sacral eschar at admission to the DIFFICULT-TO-WEAN UNIT, by measurement of resting energy expenditure by calorimetry at admission to the DIFFICULT-TO-WEAN UNIT and by measurement of lean mass, fat mass and dilution by impedancemetry at admission to the Difficult-to-Wean Unit.

5 Patient selection

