10.3 Main objective

Patients will be classified into 2 groups: success or failure of decanulation. The variables collected will be compared between the 2 groups by the appropriate tests according to the type of variables (quantitative or qualitative) and their distribution. The results of these comparisons will be used to select the variables showing a difference between the 2 groups (p < 0.20) for inclusion in the multivariate logistic regression. (24)(25)

The previously selected ultrasound variables will be included in the model predicting the success of decanulation. Multiple logistic regression with variable selection using the Akaike information criterion (AIC) method will be used. The presence of multicollinearity between variables will also be investigated and the variable eliminated if necessary.

11 Expected results in terms of scientific and professional advances

This study will determine the factors contributing to the success of decanulation in patients admitted to DIFFICULT-TO-WEAN UNIT after a prolonged ICU stay. The evaluation of these success factors will provide data that is still lacking due to the lack of literature in specialised post-resuscitation ventilatory weaning facilities.

This information may be useful in the post-resuscitation follow-up and in the prioritisation or not of early rehabilitation in these patients.

12 Expected benefits and risks for patients

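### Findings that decide whether the cannula is removed are also candidate predictors of successful decannulation, so part of their association may come from the unit's own rule

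*Combined protocol and SAP*

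**What the plan says.** **The decision rule.** Section 7.7 describes stepwise de-ventilation, then 48 hours with the cannula plugged, then extra-respiratory checks. On swallowing: "Decanulation is possible when the patient does not have a major swallowing disorder". On strength and diaphragm, decannulation is possible "when muscle recovery, absence or recovery of diaphragmatic dysfunction and trunk tone are satisfactory", and the same section names the tools: "neuromuscular and diaphragmatic function (MRC score, ultrasound) are assessed". On endoscopy, the cannula comes out "Once all the parameters are satisfactory and a decanulation fibroscopy does not reveal any anomaly contraindicating decanulation".

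**The candidate factors.** Section 4.1 lists, among the factors to be tested: "Existing swallowing disorders (assessed after 6 hours of ventilation) by the modified Cowling swallowing score"; diaphragmatic dysfunction on admission; MRC score on admission; and abnormalities at the fibroscopy done before decannulation.

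**The analysis.** Section 10.3 states: "Patients will be classified into 2 groups: success or failure of decanulation". Variables that differ at p < 0.20 enter a logistic model with AIC selection. The section does not say where a patient who was never decannulated belongs. Section 4.1 defines success by events within 48 hours and does not classify such patients either. Section 4.2 takes as a secondary outcome "Proportion of successful decanulation among all included patients", and section 10.1 obtains 100 patients by applying 60% success to all inclusions.

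**Bias control.** Section 9.4 deals with measurement bias, through assessors outside the care team. Nothing addresses the overlap between the rule and the predictors.

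**The concern.** If never-decannulated patients count as failures, a patient whose cannula stays in because of poor swallowing or an abnormal fibroscopy is a failure by that decision. The model would then return the finding as a predictor even if it had no bearing on who tolerates removal.

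Section 2 hypothesises independent factors for success, and section 1 wants them in order to select patients. A coefficient that partly restates the unit's rule would be misread as evidence about tolerance, and a unit with a different rule could not expect to reproduce it.

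**Working it through.** **1. The plan's own figure.** Section 10.1 gives 6 variables, 10 events per variable and 60% success: 6 × 10 / 0.60 = 100. This reproduces the stated 100, and it works only if the 60 successes are counted over all inclusions. That leaves 40 non-successes.

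**2. Who the 40 could be.** Section 1 quotes a 2-25% failure rate of decannulation from the literature. Assume that it applies to the same population as the local 60%. With failure rate f among those decannulated, the number decannulated is 60/(1 − f).

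| f | Decannulated | Failed after removal | Never decannulated | Share of the 40 |
|---|---|---|---|---|
| 2% | 60/0.98 = 61.2 | 1.2 | 38.8 | 97% |
| 10% | 60/0.90 = 66.7 | 6.7 | 33.3 | 83% |
| 25% | 60/0.75 = 80.0 | 20.0 | 20.0 | 50% |

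**3. How close each predictor is to the rule.**

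- *Fibroscopy:* the same examination in both roles. Section 9.3 records whether it was done at all, so it may be missing for patients who never reach that stage.
- *Swallowing:* the same domain, but the rule bars a major disorder while the predictor is a four-level score. Section 7.5 times the assessment to several hours per day off the ventilator; sections 9.2.2 and 9.5 list it at inclusion.
- *MRC score and diaphragm:* admission values, while the rule looks at later status and accepts recovery. The link runs only through dysfunction that persists.

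**4. Illustration with assumed inputs.** Suppose that a factor has no effect on tolerance, success is otherwise 70%, and the rule holds back a share b of carriers. Success in carriers is then 0.70 × (1 − b).

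- b = 20%: 0.56; OR = (0.56/0.44)/(0.70/0.30) = 1.273/2.333 = 0.55.
- b = 40%: 0.42; OR = (0.42/0.58)/(0.70/0.30) = 0.724/2.333 = 0.31.

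For overall success to stay at 60%, carriers would have to make up 0.10/0.14 = 71% or 0.10/0.28 = 36% of patients.

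A second version fixes overall success at 60%, sets carriers at 20-40% and holds back 25% of them. The OR is 0.50-0.53, and such a null factor passes the p < 0.20 screen in the unfavourable direction with probability about 0.50-0.65, against 0.10 with no holding back.

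**5. Does restricting to decannulated patients cure it?** No. In a simulation of 2,000,000 patients (30% carriers; removal when a latent readiness score passes a threshold set 0.5 or 1.0 SD higher for carriers), a factor with a true OR of 1.0 gave 0.65 or 0.37 over all included patients. Among decannulated patients it gave 1.30 or 1.82. A true OR of 0.56 became 0.68 or 0.93 among the decannulated.

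**The case against.** The strongest reply is that the objective is factors associated with success under unchanged usual care, not causes of tolerance. An admission factor that predicts success partly through the team's decision can still help to prioritise rehabilitation, as section 11 intends. This stands. It limits what may be concluded and does not invalidate the analysis.

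Second, section 10.3 never says that all included patients form the denominator. That is inferred from sections 4.2 and 10.1. If the sponsor means decannulated patients only, the mechanism changes: the same rule then selects the sample, with the distortion shown in step 5.

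Some stronger readings are tempting and are not supported:

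- *That 50-97% of failures are produced by the rule.* The table counts patients never decannulated, not patients held back by these criteria. The extra-respiratory checks come only after full de-ventilation and 48 hours plugged. Patients who die, return to intensive care or are never weaned do not reach them. The range also joins a literature rate to a local estimate.
- *That the odds ratios are estimates for this cohort.* The documents give neither the prevalence of these disorders nor how often they block removal.
- *That all four domains are equally affected.* Step 3 shows otherwise.
- *That sections 7.7 and 8 contradict each other on ultrasound.* Section 12.1 ties the added burden to the initial assessment, so the research scan and the decision-time assessment can be read as different examinations. It remains true that no section withholds the research result from the team. Section 9.4 and the safeguard in section 8.1 concern who measures and what happens during the scan.

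**Conclusion.** The overlap is explicit, and the plan does nothing about it. Under the denominator that sections 4.2 and 10.1 imply, some of the association for these variables can come from the decision rule. The case is clear for fibroscopy, plausible for swallowing and weaker for MRC score and diaphragm.

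The size cannot be fixed from the documents. About 20-39 of 40 non-successes would never have been decannulated if the two quoted rates share a population, and an unknown part of these were held back by the four criteria. The odds ratios of 0.55 and 0.31 show only that modest holding back is enough to create a sizeable association.

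The change should be made before analysis. It concerns what is reported and how it is labelled; the cohort keeps its value for describing who succeeds under this unit's practice.

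**What to change.** In section 10.3:

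1. State that the denominator is all included patients.
2. Report non-success in two parts: *never decannulated*, with the reason, and *decannulated, then failed within 48 hours*. The number of decannulations and the mode of discharge in section 9.3 already support most of this. A patient held back by a specific criterion would need the reason taken from the record.
3. Leave pre-decannulation fibroscopy out of the all-included multivariable model and describe it among the patients examined.
4. Keep swallowing as a candidate, and fit the model with and without it. Excluding it outright would discard a prespecified factor whose overlap with the rule is only partial.
5. Label the swallowing, MRC and diaphragm associations as predictors of success under the unit's decision protocol, not of tolerance of decannulation.
6. Mark any table within decannulated patients as descriptive only. It would rest on about 1-20 failures, and selection by the same rule can weaken a real association or make a null factor look favourable.

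A secondary improvement is to record whether the team knew the research ultrasound result when deciding.

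The cost is one extra table, one sensitivity model, some wording and a narrower conclusion. No clinical rule changes.

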8.1 Ultrasound measurements

The ultrasound measurements will be performed by one of the physiotherapists or investigating physicians. The physiotherapist is entitled to perform ultrasound subject to training (21).

All the physiotherapists investigators have been trained according to the teaching recommendations for lung ultrasound (22) and are already involved in other research projects using lung and diaphragm ultrasound (https://clinicaltrials.gov/ct2/show/NCT02474797 and https://clinicaltrials.gov/ct2/show/NCT02881814).

When a physiotherapist performs an ultrasound scan, a referring resuscitation physician will be present to control the execution of the examination and to ensure that the recommendations of practice are respected. He will also ensure that the patient's management is not modified during the examination. The referring resuscitators are resuscitators trained in ultrasound (either through a diploma, qualifying training or acquired during their clinical experience) and named below [name] [name], [name] [name] and [name] [name].

